10.1 Statistical Hypotheses

Aim 1:

Hypothesis: Among adults with hypertension recruited from an outpatient clinical setting, 4 weeks of continuous home PAC use, compared with sham PACs, will be associated with decreased concentrations of TNF α when measured before and after intervention.

Aim 2:

Hypothesis: Reductions in measured PM_{2.5} from PAC use will be associated with decreased concentrations of circulating TNF α

10.2 Analysis Datasets

These analyses will be conducted as Intention-to-Treat dataset. Per-Protocol Analysis will be explored if electricity monitor data indicates poor compliance with PAC usage (if electricity monitor recordings indicate kilowatt-hour usage that is lower than expected by 50%).

10.3 Statistical Methods

Aim 1 Analysis.

Descriptive summary statistics, such as mean and standard deviation (or median and inter quartile range) will be reported for continuous variables and counts and proportions for categorical variables. Graphical displays of all variables will be examined, with attention to assessing balance in these characteristics by intervention group, and with assessment of the distribution of variables, relevant to the choice of statistical tests. Statistical comparisons between the PAC and sham groups will be performed using a two-group two-sided t-test or nonparametric Wilcoxon test for continuous variables and Chi-square test for

categorical variables. Distributions of biomarker concentrations will be examined, and non-normally distributed concentrations will be log-transformed, as needed.

The analysis of our primary outcome will use linear mixed-effects models with the change in prespecified biomarker, from pre-intervention to post-intervention, concentrations as the dependent variable and treatment arm as the independent variable. While randomization should obviate the need for additional adjustment, models will be adjusted for age, gender and BMI, as these are known to be related to inflammatory biomarker concentrations.^{20, 21} These models use subject-specific random intercepts to account for heterogeneity between subjects and will account for within subject correlation between biomarker observations. The proposed model is:

$$\Delta TNF\alpha = \beta_1 + \beta_2(PAC\ arm) + \beta_3(age_i) + \beta_4(gender_i) + \beta_4(BMI_i) + e_i$$

We will also utilize similar models incorporating PM_{2.5} as the independent variable in place of PAC arm. This will be assessed as the difference between pre-intervention baseline PM_{2.5} concentration and the time-weighted average concentration of PM_{2.5} from the 14-day intervention period. For our exploratory aim we will evaluate the Olink panel results using mixed-effects models for the remaining biomarkers that were not prespecified. Additionally, we will explore associations of PAC use with measured blood pressure in this clinical cohort that likely differs from our current pilot cohort recruited from a community setting. Because this pilot will integrate with our larger R01 trial, for which blood pressure is the primary outcome of interest, we will incorporate this biomarker data into that trial for a secondary exploratory analysis of biomarkers as mediators in the association between PAC use and blood pressure reductions.

In our exploratory analysis, there will be multiple testing bias due to utilizing a panel of 369 possible biomarker outcomes. With this size pilot cohort, it will be unlikely to achieve statistical significance if strict adjustments for multiple testing are undertaken. However, we will use the Holm procedure to evaluate for significance. Overall, these exploratory analyses will be hypothesis-generating and can help inform the design and sample size of future cohorts.

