Statistical Analysis	
For all Aims: descriptive summary statistics, such as mean and standard deviation (or median and inter quartile range) will be reported for continuous variables and counts and proportions for categorical variables. Graphical displays of all variables will be examined, with attention to assessing balance in these characteristics by intervention group, and with assessment of the distribution of variables, relevant to the choice of statistical tests. Statistical comparisons between the PAC and sham groups will be performed using a two-group two-sided t-test or nonparametric Wilcoxon test for continuous variables and Chi-square test for categorical variables. Distributions of biomarker concentrations will be examined and non-normally distributed concentrations will be log-transformed, as needed.
 
The analysis of our primary outcome for Aim 1 will use linear mixed-effects models with the change in prespecified biomarker, from pre-intervention to post-intervention, concentrations as the dependent variable and treatment arm as the independent variable. While randomization should obviate the need for additional adjustment, models will be adjusted for age, gender and BMI, as these are known to be related to inflammatory biomarker concentrations. These models use subject-specific random intercepts to account for heterogeneity between subjects and will account for within subject correlation between biomarker observations.
 
For Aim 2, we will also utilize similar models incorporating $PM_{2.5}$ as the independent variable. This will be assessed as the difference between pre-intervention baseline $PM_{2.5}$ concentration and the time-weighted average concentration of $PM_{2.5}$ from the 14-day intervention period.
 
For Exploratory Aim 1, we will evaluate the Olink panel results using mixed-effects models for the remaining biomarkers that were not prespecified. These will be the same models as for Aims 1 and 2, adjusted for age, gender, and BMI. For Exploratory Aim 2, we will evaluate associations of PAC use and $PM_{2.5}$ reduction with measured AM systolic blood pressure in this clinical cohort. We will perform mediation analysis using biomarkers with significant associations in Exploratory Aim 1 as mediators of the relations between $PM_{2.5}$ reduction and change in blood pressure.

Schematic of Study Design

1 Key Roles

Principal Investigator

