4.1 Description of Study Design

In this research, we will conduct a randomized, double-blind, sham-controlled pilot trial to study the effect of PAC use on the concentrations of circulating biomarkers of inflammation in outpatient adults within the NYU Langone Health system.

Aim 1: To determine if 4 weeks of home air filtration with PACs compared to sham is associated with significant reductions in TNF α concentrations when measured before and after intervention.

Data collection will begin Q2 2022 with a total of two time points 4 weeks apart, pre- and post-intervention. The study design utilizes purposeful selection of 74 adults with stable hypertension within the NYU Langone health system outpatient cohort. We will define stable hypertension as no medication changes in prior 30 days, systolic BP <160 mm Hg and either \geq 130 mm Hg without antihypertensive medications, or diagnosis of hypertension in medical records. Per guidelines, this range is considered safe to monitor without changes in antihypertensive medications. At the initial clinic visit, blood will be collected and stored for analysis. We will measure circulating concentrations of TNF α using the Olink Explore 384 Cardiometabolic panel for this *a priori* specified analysis; this panel will also measure the concentrations of other biomarkers that we will explore further in Exploratory Aims 1 and 2. The Olink analysis uses a Proximity Extension Assay that has been shown to have high specificity and accuracy to allow for assessment of changes in concentrations between repeated samples over time.^{18, 19}

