7.4 Enrollment/Baseline

Enrollment/Baseline Visit (Visit 1)

- Verify inclusion/exclusion criteria
- Answer questions from potential participants regarding the air monitors, PACs and BP monitors to verify interest in participating
- Obtain written consent from eligible participant
- Schedule study visits (video visit for setup and clinical visit 2 for second blood draw) for individuals who are eligible and available to participate for the full duration of the study
- Record participant BP, height, weight, and waist circumference if not done as part of clinical visit
- Collect blood for baseline biomarker measurement pre-intervention: <15 mL for all, additional ~10 mL for participants opting into future research.

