10.4 Sample Size

Power Analysis: While we do not expect substantial participant dropout over this short trial, our power analyses include adjustment for up to 10% dropout in each arm. Based on our meta-analysis of biomarkers²², we estimate a 10% change in concentration of biomarkers with PAC use versus sham.^{13 13} Using a basic multiple regression model incorporating age, BMI, and gender, along with our exposure (active PAC vs sham), we will have greater than 80% power to reject the null hypothesis of zero effect size at the significance level (alpha) of 0.05, with a sample size of 66. As such, our enrollment goal of 44 participants, limited by budgetary constraints, may provide sufficient power to detect significant changes in biomarker concentrations. However, in the event that we are not able to reach statistical significance with the changes we detect, these results will still be informative for developing future studies. We will include baseline-only data for participants who do not complete the protocol.

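### The primary TNFα model leaves out baseline TNFα and does not fix the outcome scale; the cost is precision, not bias, and its size cannot be set from the documents

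*Combined protocol and SAP*

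**What the plan says.** Section 10.3 describes the Aim 1 analysis as "linear mixed-effects models with the change in prespecified biomarker, from pre-intervention to post-intervention, concentrations as the dependent variable". On covariates it states that "models will be adjusted for age, gender and BMI, as these are known to be related to inflammatory biomarker concentrations". The printed equation has arm, age, gender, BMI and a residual. Neither the text nor the equation has a baseline TNFα term, and the Protocol Summary describes the same model. Section 7.4 provides for the measurement: "Collect blood for baseline biomarker measurement pre-intervention", from all participants.

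The outcome scale differs by place:
- Section 4.2.1 defines the primary endpoint as percent change from the pre-intervention value.
- The Protocol Summary (Endpoint) and section 10.3 refer to change in concentration.
- Section 10.3 adds that non-normal concentrations will be log-transformed if needed.

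Section 4.1 sets out data collection "with a total of two time points 4 weeks apart, pre- and post-intervention", which yields one change value per person. Section 10.3 nevertheless says "These models use subject-specific random intercepts to account for heterogeneity between subjects", and that the models "will account for within subject correlation between biomarker observations". The power statement in section 10.4 rests on a simpler model: "Using a basic multiple regression model incorporating age, BMI, and gender", plus arm. The same section promises to include baseline-only data from participants who do not finish.

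**The concern.** The plan picks covariates because they relate to inflammatory biomarkers. A participant's own pre-intervention TNFα is the obvious candidate on that reasoning, and it is already paid for. Subtracting baseline does not replace adjusting for it: when pre and post variances are equal, change is correlated with baseline whenever r is below 1, and that correlation stays in the residual. Precision matters here because section 10.4 calculates a need for 66 and then gives "our enrollment goal of 44 participants, limited by budgetary constraints".

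The scale is a prespecification matter. Percent change, absolute change and log change are different dependent variables. With the transformation left to inspection of the data, the primary P value does not come from one fixed analysis.

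**Working it through.** **Inputs from the documents.** 10% effect, alpha 0.05, power above 80% at 66, 10% dropout, and a regression with three covariates plus arm (section 10.4); 1:1 allocation (section 10.5.1). Enrolment is 44 in section 10.4 and 74 in sections 4.1 and 5.6. I read 66 as evaluable because 74 × 0.9 = 66.6. With 44 enrolled, 44 × 0.9 = 39.6, or about 40 evaluable.

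**Assumptions.** Two-sided test, exactly 80% power at 66, equal pre and post variances, and r from 0.3 to 0.9.

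**Step 1: the plan's own figure.** The 66 cannot be reproduced, because no SD or standardised effect is given, so it is back-solved. Power comes from a noncentral t with df = N − 2 − k (k covariates) and noncentrality Δ√N/(2 × SD). With N = 66, k = 3, df = 61 and Δ = 10 points, 80% power requires an SD of change of 14.27 points (d = 10/14.27 = 0.701). The same model then has 62.1% power at 44 and 57.7% at 40.

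**Step 2: effect of adding baseline.** With between-person SD σ, the variance of change is 2σ²(1 − r). The baseline-adjusted residual variance is σ²(1 − r²). The ratio is (1 + r)/2, which never exceeds 1. With the change SD held at 14.27 and k = 4:

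| r | Variance ratio | Implied σ (points) | Power at 40 (57.7% unadjusted) | Power at 44 (62.1%) | Power at 66 (80.0%) |
|---|---|---|---|---|---|
| 0.3 | 0.65 | 12.1 | 76.1% | 80.2% | 93.5% |
| 0.5 | 0.75 | 14.3 | 70.1% | 74.4% | 89.9% |
| 0.7 | 0.85 | 18.4 | 64.6% | 69.0% | 85.9% |
| 0.9 | 0.95 | 31.9 | 59.8% | 64.2% | 82.0% |

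**Step 3: simulation.** The closed form ignores chance correlation between arm and the covariates. Simulating a true ratio of 0.90, an SD of log change of 0.150 and three random covariates (4,000 runs per cell) gives lower power:
- At 40: percent change 54 to 55%; log ANCOVA 72%, 64%, 60% and 55% for r = 0.3, 0.5, 0.7 and 0.9.
- At 44: percent change 59 to 60%; log ANCOVA 77%, 69%, 65% and 61%.
- Percent change with log baseline as a covariate is within 1 point of log ANCOVA in these cells.

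The gain is therefore about 17 to 18 points at r = 0.3 and 0 to 2 points at r = 0.9.

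**Step 4: a different anchor for the SD.** Step 2 fixes the change SD, so a low r forces participants to be nearly alike. Fix σ at 30 points instead (an assumption), with N = 44 and the closed form:

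| r | SD of change, 30√(2(1 − r)) | Unadjusted | Adjusted | Gain (points) |
|---|---|---|---|---|
| 0.3 | 35.5 | 14.9% | 20.4% | 5.5 |
| 0.5 | 30.0 | 19.0% | 23.8% | 4.8 |
| 0.7 | 23.2 | 28.5% | 32.6% | 4.1 |
| 0.9 | 13.4 | 67.4% | 69.6% | 2.2 |

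**Step 5: a smaller effect.** Section 2.1 cites TNFα as 2% lower with filtration, not statistically significant. With Δ = 2 and SD 14.27, power at r = 0.3 goes from 7.2% to 8.3% at 40, and from 7.4% to 8.7% at 44. At higher r the gain is smaller.

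**Step 6: dependence on exactly 80%.** If power at 66 were 90% (d = 0.811), the closed form at 40 would be 70.3% unadjusted and 87.1%, 82.0%, 77.1% and 72.4% adjusted, in the same r order.

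**Step 7: random intercept.** With one change value per person, the intercept and residual variances cannot be separated. Fitting such a model to 44 simulated change values split the variance into two equal parts (115.76 each), with a Hessian that was not positive definite. The arm estimate and its standard error are unaffected.

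**The case against.** The strongest reply is that a covariate-adjusted change score is a valid analysis under randomisation, that section 10.4 openly accepts a budget-limited pilot may miss significance, and that the gain is unknown. All of that stands. If 74 is the true enrolment, about 66 complete and the gain is only extra margin. The reply does not give a reason to leave out a covariate that is already measured and costs one degree of freedom, and a tighter interval serves the plan's stated aim of informing later studies.

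On scale, section 4.2.1 can be read as the governing definition, with the Protocol Summary a short label. Percent change and log change also have nearly equal power in simulation (55.0% and 55.3% at 40, r = 0.3). So the inconsistency is not shown to distort the result much. Under the null at 40 evaluable, always taking the smallest P value of absolute, percent and log change gave a type I error of 5.5 to 6.4%, which is a worst case. The open log rule is still worth closing.

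On the random intercept and baseline-only data, the wording may point to an intended two-visit mixed model, which baseline-only participants can enter. They are excluded only if the printed single-change equation is taken literally. These are secondary wording points.

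A reader might infer that adding baseline TNFα would bring 44 participants up to 80% power. The closed form suggests so at r = 0.3 (80.2%), but simulation gives 75 to 77% there and reaches 80% only near r = 0.2. At 40 evaluable it gives 78% even at r = 0.1.

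**Conclusion.** The concern holds as a matter of efficiency and prespecification. The planned arm comparison is unbiased, and it is no more precise, and usually less precise, than a baseline-adjusted one. The documents do not support calling the primary analysis biased or invalid.

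No single figure for the gain can be defended, because neither the SD nor r is given:
- Change SD 14.3 points, effect 10 points, 40 to 44 evaluable: about 17 to 18 points of power at r = 0.3, and 0 to 2 at r = 0.9.
- Between-person SD 30 points, effect 10 points, 44 evaluable: about 2 to 6 points.
- Effect 2 points, change SD 14.3: about 1 point or less.

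Baseline adjustment should not be presented as restoring 80% power. Taking exactly 80% at 66 evaluable, that needs r of about 0.2 or lower at 44 and is not reached at 40 even at r = 0.1. The change is worth making because it is nearly free, not because a large gain is assured.

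**What to change.** 1. Add baseline TNFα, on the log scale, as a covariate in the primary model of section 10.3 and in the similar PM2.5 models for Aim 2. Carry this into the Protocol Summary.
2. Fix one outcome scale before unblinding. Either keep the percent change of section 4.2.1 with log baseline as a covariate, or model log post-intervention TNFα on log baseline and report a percent difference (ratio of geometric means). The first leaves the endpoint definition untouched; the second re-expresses it.
3. Remove the discretionary log rule for the primary outcome, so that the Protocol Summary, section 4.2.1 and section 10.3 agree.
4. As secondary wording, choose one reading. Either drop the random-intercept and within-subject-correlation sentence and call baseline-only data descriptive, or state a two-visit mixed model with a common baseline mean and replace the printed equation.

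The cost of the covariate is one residual degree of freedom (34 instead of 35 at 40 evaluable). No new data are needed. Section 13.2 requires IRB approval of the amendment before it takes effect.

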Brief Summary	
In this research, we will conduct a double-blind, sham-controlled, randomized trial to examine the impact on cardiometabolic biomarkers of air pollution exposure reduction using home portable air cleaners (PACs) in a cohort of current adult patients at NYU Langone Health. This study is funded by CTSI (NIH/NCATS UL1TR001445) with two primary aims and two secondary/exploratory aims. In Aim 1, we will evaluate associations with PAC use with a priori specified biomarker of inflammation, tumor necrosis factor alpha (TNFα). We will determine if 4 weeks of home air filtration with PACs compared to sham is associated with significant reductions in TNFα concentrations when measured before and after intervention. Blood samples will be collected from 44 study participants before and after 4 weeks of PAC use (true and sham) for biomarker concentration measurement. In Aim 2, we will determine if reductions in fine particulate matter (<2.5 μm in diameter, PM_{2.5}) as a continuous variable are associated with significant reductions TNFα concentrations over a four-week period. In Exploratory Aim 1, we will explore associations between PAC use and concentrations of cardiometabolic biomarkers using a targeted proteomic panel, the Olink Explore 384 Cardiometabolic panel, measured before and after 4 weeks of intervention. This will be a hypothesis-generating analysis to identify possible novel biomarkers and pathways that may have importance in the physiological responses and clinical outcomes associated with air pollution exposure. In Exploratory Aim 2, we will explore if biomarkers identified in Exploratory Aim 1 with significant reductions after 4 weeks of PAC partially mediate the association between reductions in PM_{2.5} and changes in daily home blood pressure (BP) measurements. Participants will be given home BP monitors to transmit de-identified daily morning BP measurements to a secure database during the 4 week intervention period. Changes in morning systolic (BP) will be analyzed as the outcome of interest, with changes in biomarker concentrations evaluated as a mediator of the relations between pollution reduction and changes in BP.

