Objectives	
The primary objective of this research is to examine how PACs that reduce air pollution exposure affect cardiometabolic biomarkers and how those may mediate relationships with cardiovascular risk factors such as hypertension.
 
Specific Aim 1: To determine if 4 weeks of home air filtration with PACs compared to sham is associated with significant reductions in TNFα concentrations when measured before and after intervention.
 
Specific Aim 2: To determine if reductions in PM_{2.5} are associated with significant reductions TNFα concentrations over a four-week period.
 
Exploratory Aim 1: To identify novel biomarkers of the cardiometabolic effects of PM_{2.5} exposure with PAC use with a targeted proteomic panel, the Olink Explore 384 Cardiometabolic panel, measured before and after 4 weeks of intervention.
 
Exploratory Aim 2: To determine if novel biomarkers identified in Exploratory Aim 1 are mediators of the relationship between PAC use and home BP reductions after 4 weeks of PAC use.

Methodology	Randomized, double-blind, sham-controlled pilot study
Endpoint	
Aim 1 primary endpoint: Change in circulating concentration of TNFα
 
Aim 2 primary endpoint: Change in indoor PM_{2.5} concentration
 
Exploratory Aim 1 primary endpoint: Change in concentration of 384 circulating biomarkers associated with cardiometabolic risk
 
Exploratory Aim 2 primary endpoint: Change in average AM systolic blood pressure over study period

Study Duration	4 weeks
Participant Duration	Maximum: 4 weeks

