Population	We will perform a randomized, double-blind, sham-controlled trial of continuous (24 hours/day) bedroom PAC use in an outpatient cohort English and Spanish speaking adults ≥ 18 years of age with stable hypertension (defined as no medication changes in prior 30 days, systolic BP < 160 mm Hg and either ≥ 130 mm Hg without antihypertensive medications, or diagnosis of hypertension in medical records). Per guidelines, this range is considered safe to monitor without changes in antihypertensive medications. Additional inclusion criteria require participants to measure home blood pressure twice daily, participate in video conference for home equipment setup, and ability to visit clinic for blood draws before and after the study period. Participants will be excluded if they are current smokers, currently have known coronary artery disease, have known systemic inflammatory conditions (such as rheumatoid arthritis, inflammatory bowel disease, cancer), or are currently taking any anti-inflammatory medications or medications that target inflammatory cytokines. We aim to enroll 44 participants, randomized in a 1:1 ratio to PAC with HEPA filtration versus sham filtration.

Study Sites	Participants will be consented and enrolled at NYU outpatient clinic facilities in Manhattan. At this visit, patients will have baseline blood drawn and will receive all study equipment. Participants will set up air pollution monitor and PAC in their homes with video chat guidance. PAC will be run continuously in participant bedrooms for 4 weeks. Participants will have follow-up visit to NYU Langone hospital clinical lab for post-intervention blood collection and equipment return.
Number of participants	To achieve 44 study participants, we will need to identify \approx 300 eligible participants from the electronic health record (EHR) in NYU clinics. There will be 22 participants per arm (sham versus active filtration).

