
2.2 Rationale

Because PAC use has been associated with decreases in concentrations of circulating CRP and IL-6, we hypothesize the following: (1) Among adults with hypertension recruited from an outpatient clinical setting, 4 weeks of continuous home PAC use, compared with sham PACs, will be associated with decreased concentrations of TNF α when measured before and after intervention; (2) Reductions in measured PM_{2.5} from PAC use will be associated with decreased concentrations of circulating TNF α .

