We will randomize participants to receive PAC with either true or sham filtration (HEPA filter removed). Equipment will be shipped to participant homes or given to participant at clinical visit along with written instructions for setup and use. Active and sham PACs, and pollution monitors, will be positioned in the bedroom where each participant sleeps. We will video conference with participants for initial setup of equipment, though prior data suggests that written instructions alone are effective in aiding participants in this process. We will use a commercially available portable air cleaner with a “true HEPA” filter for the true arm. For the sham arm, the same model will be used with HEPA filter removed, and has identical appearance and sound. After enrollment and baseline blood draw, Home BP will be monitored using commercially available device with a paired data hub that transmits BP measurements to an online dashboard in real time. We will monitor participant adherence to PAC use with electricity consumption monitors. Participants will be scheduled for a clinic visit after 4 weeks of PAC use to return data hubs, electricity monitors and pollution monitors to the study team, and will undergo post-treatment blood draw. A second blood draw will be performed and blood will be stored for analysis. Participants will receive reimbursement after equipment is returned and second blood draw is complete. Participants randomized to sham PAC arm will receive HEPA filters to install and keep.

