6.1.4 Duration of Therapy

The PACs will be run continuously (24 hours per day) in participants' bedrooms for 4 weeks.

7 Study Procedures and Schedule

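### Aim 2 relies on a pre-intervention PM2.5 baseline that no available section defines or requires to be recorded, and the Attachment C setup order would leave none

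*Combined protocol and SAP*

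**What the plan says.** The Protocol Summary describes the study as funded "with two primary aims and two secondary/exploratory aims", and Aim 2 is one of the two primary ones. Its hypothesis (sections 2.2 and 10.1) is that reductions in measured PM2.5 "from PAC use will be associated with decreased concentrations of circulating" TNFα.

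The exposure is defined in section 10.3 and repeated in the Protocol Summary under Statistical Analysis: "This will be assessed as the difference between pre-intervention baseline" PM2.5 and a time-weighted average "from the 14-day intervention period". Section 4.2.2 also uses PM2.5 change for Exploratory Aim 2, counted from a baseline that it does not describe further. Section 6.1.4 has the PACs running in participants' "bedrooms for 4 weeks".

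On setup:

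- The Protocol Summary (Study Sites) says "Participants will set up air pollution monitor and PAC in their homes with video chat guidance".
- Section 4.1 commits to a video conference for initial setup and adds that "prior data suggests that written instructions alone are effective in aiding participants in this process".
- Section 7.5 places the PAC and the PM monitor at the same video visit and requires switch-on no later than 7 days after the baseline draw.
- Attachment C tells the participant to turn the PAC on and leave it on throughout, and in later bullets to hang the PM monitor and plug it in.

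The documents also differ on what PM2.5 change is. The Protocol Summary lists "Aim 2 primary endpoint: Change in indoor" PM2.5 concentration, whereas section 4.2.1 gives percent change in TNFα as the primary endpoint of both aims.

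**The concern.** A difference from baseline needs readings taken before the intervention starts. Here the monitor reaches the bedroom together with the device whose effect it is meant to measure, and no available section says that it runs first.

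If those readings are not taken, they cannot be recovered at analysis. Early readings after switch-on are not a neutral substitute. In the active arm they would already reflect HEPA filtration and in the sham arm they would not, so the active-arm reduction could be understated.

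The gap would also come to light late. Section 4.1 retrieves the PM data from SD cards at the final visit, and section 10.5.1 downloads them after the participant has finished. Section 7.5 connects the monitor to WiFi where available, but no section uses that connection to check for readings before switch-on.

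At stake are the Aim 2 model, the Exploratory Aim 2 endpoint in section 4.2.2, and the mediation analyses framed by PM2.5 change.

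**Working it through.** The plan gives no figure for the baseline, so there is nothing to reproduce. The check is a comparison of sections, followed by a count of the readings the text allows.

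**Where a baseline could be specified**

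| Place | What it provides | PAC-off PM2.5 recording? |
|---|---|---|
| 7.4 Enrollment/Baseline | Consent, BP, height, weight, waist, blood | No |
| 7.5 Video Visit | PAC and monitor placed; switch-on limit tied to the blood draw | Permitted, not required |
| 7.6 Final Study Visit | Equipment return, second draw | No |
| 4.1, Aim 2 | Sensor type, 2-minute sampling, retrieval | No |
| 10.5.1 | Download and blinded processing | No |
| Attachment C | PAC on, then monitor plugged in | Excluded if followed in the listed order |

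None of the 3 visit sections specifies PAC-off recording, and none of the six places says which readings form the baseline.

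**Readings before switch-on.** Inputs are one reading per 2 minutes (4.1, Aim 2), switch-on within 7 days of the draw (7.5) and a 15-minute setup visit (5.5).

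- Per sensor per day: 24 × 60 / 2 = 720.
- If setup falls on day s after the draw, the longest possible PAC-off period is 7 − s days, giving (7 − s) × 720 readings:

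| s | PAC-off days, at most | Readings per sensor, at most |
|---|---|---|
| 0 | 7 | 5,040 |
| 4 | 3 | 2,160 |
| 5 | 2 | 1,440 |
| 6 | 1 | 720 |
| 7 | 0 | 0 |

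- If the monitor is started first but the PAC is switched on within the setup visit: 15 / 2 = 7.5, so at most about 7 readings.
- In the Attachment C order: 0 readings.

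The range is therefore 0 to 5,040. The upper end needs setup on the day of the draw and switch-on at the 7-day limit, which no section asks for.

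**Averaging period.** 14 days give 14 × 720 = 10,080 readings and 28 days give 28 × 720 = 20,160, a ratio of 0.50. If recording runs to the 35-day limit for the final draw (7.6), 35 × 720 = 25,200 and the ratio is 0.40. Read literally, the 14-day wording uses half or less of the intervention record and does not say which half.

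**The case against.** The strongest reply is that the order of bullets proves little. Attachment C is unnumbered, section 19 places it outside the protocol, and its device numbers do not match its own list. Section 7.5 puts its switch-on bullet last, and the Protocol Summary names the monitor before the PAC. Setup is also staff-guided: section 4.1 promises a video conference, section 5.1 makes it an inclusion criterion, and the remark about written instructions belongs to that same sentence. Staff could start the monitor first, and section 7.5 leaves room for up to 7 PAC-off days.

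Much of this stands. A reader might infer that the trial plans to collect no PM2.5 baseline, or that participants will follow Attachment C alone. The documents support neither reading: they show setup texts that have not been reconciled. A run-in drawn only in the schematic cannot be excluded either, although Attachment C would then conflict with it. What the reply does not supply is any sentence that requires recording before switch-on or defines the baseline.

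Three further limits are fair. The 14-day wording is a separate contradiction in the same sentence and adds no weight to the baseline gap. The counts show what the text allows, not how far the Aim 2 estimate would move. And Aim 2 is a non-randomised exposure-response analysis in a pilot; even so, the plan labels it primary.

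**Conclusion.** The point holds as a gap in definition and schedule. The Aim 2 exposure depends on pre-intervention PM2.5, yet the available text neither requires nor defines it. For any participant set up in the Attachment C order, the exposure cannot be computed as written. The text is compatible with 0 to 5,040 baseline readings per sensor. This is more than missing detail, because a written setup order can lose data that the analysis cannot replace. The 14-day wording contradicts the 4-week intervention and would use 50% of a 28-day record.

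Two stronger readings should be avoided. First, one might say that the Aim 2 endpoint cannot be computed. Under section 4.2.1 the endpoint is TNFα change and PM2.5 is the exposure; only the Protocol Summary says otherwise, and that conflict needs resolving. Second, one might extend the problem to the whole trial. The randomised Aim 1 comparison, its TNFα endpoint, the power statement and mediation framed by PAC use do not depend on the PM2.5 baseline.

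The conclusion rests on the available text, without the schematic, and on the stated 2-minute sampling. It uses no assumed concentrations or filter performance.

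**What to change.** 1. Reconcile section 7.5 and Attachment C so that the PM monitor is running before the PAC is switched on, for a recording period whose length the sponsor sets within the existing 7-day limit.
2. In section 10.3 and the Protocol Summary, define baseline PM2.5 as the mean of those pre-switch-on readings. State that participants without them are left out of the Aim 2 change model, counted by arm, and kept in Aim 1.
3. Reconcile the 14-day wording in both places with the 4-week intervention, so that the average covers the actual intervention period, and state whether it ends at day 28 or at the final draw.
4. Reconcile the Protocol Summary with section 4.2.1 on whether PM2.5 change is the Aim 2 endpoint or its exposure.

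The cost is edited setup text, a prompt to switch the PAC on, and video visits early enough to leave room for the recording period. The equipment is already supplied. The gap between the baseline TNFα draw and PAC start becomes somewhat longer but stays within 7 days; this is the only effect on Aim 1.
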